The VA Maryland Health Care System (VAMHCS) desires to test secure messaging in My HealtheVet (MHV) for communication with research participants in the IRB approved (HP-60526), VA Funded Stroke Rehabilitation Trial "Translating Intensive Arm Rehabilitation in Stroke to a Telerehabilitation Format" aka TeleBATRAC. We are working collaboratively with the Veterans and Consumers Health Informatics Office, VHA Office of Analytics, VA Office of Connected Care, and the Office of Research and Development. We aim to assess potential and specific concerns articulated by our national collaborations, which have included: Secure Messaging triage team naming conventions, procedures for the registration, authentication and secure messaging Opt-In for veteran and non-veteran research participants, association with the study triage team, training of study participants and research triage team recipients, informed consent (to include visibility of secure messaging research communication and data to clinical management teams), management of messages and retention of data, ease of message reassignment, the identification of unintended consequences, and development and collection of data and information to inform future VA research policy and guidance.

MyHealtheVet Secure Messaging Pilot Aims and Hypotheses

Aim 1: To develop and pilot test a Home-based stroke rehabilitation program using the MHV patient portal and secure messaging as the communication delivery system.

Aim 2: To assess for differences in eHealth literacy and self-efficacy between the Delayed Entry Usual Care and the Home-based rehabilitation group using MHV secure messaging.

Hypothesis 1: Home-based MHV stroke survivor & caregivers' intervention group Web-Based Learning Self-Efficacy Scores will meet or exceed the Delayed Entry Usual Care group.

Hypothesis 2: Home-based MHV stroke survivors and caregivers' intervention group eHEALS Health Literacy Scale will meet or exceed the Delayed Entry Usual Care group scores.

Aim 3: Determine efficacy of the two (2) one-hour structured MHV training on stroke survivors and caregivers Web-Based Learning Self-Efficacy Scores (WBLSES) and eHEALS scales.

Hypothesis 1: Home-based MHV stroke survivors and caregivers' intervention group WBLSES will exceed the baseline scores at the end of the clinical trial demonstrating improved comfort and skill in using the MHV patient portal.

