Hypothesis 2: Home-based MHV stroke survivors and caregivers intervention group eHEALS Health Literacy Scale will exceed the baseline scores at the end of the clinical trial demonstrating improved comfort and skill in using secure messaging for health care management.

Aim 4: Determine efficacy of stroke survivors and caregivers use of the MHV patient portal and Secure Messaging for communication with research team.

Hypothesis 1: Home-Based MHV stroke survivors and caregivers intervention group WBLSES and eHeals literacy scores will increase from baseline demonstrating improved comfort and skill in the use of the MHV patient portal and secure messaging for health care management.

Hypothesis 2: Home-Based MHV stroke survivors and caregivers secure messaging volume will increase over the 18 week period of the study demonstrating improved comfort and skill in the use of secure messaging and enhanced self-efficacy for self-regulated stroke rehabilitation.

2 * Discuss the research design including but not limited to such issues as: probability of group assignment, potential for subject to be randomized to placebo group, use of control subjects, etc.:

This is a longitudinal, single blind, randomized controlled trial with three parallel 6 week intervention arms conducted over a three-year time period :

1) Home-based BATRAC Telerehab (HBT) + TTT, 2) Lab-based BATRAC (LBB) + TTT, and 3) Delayed Entry Usual Care group that will serve as a control for the initial six weeks of enrollment and NOT receive an active study intervention before randomizing to one of the two active interventions. This strategy will ease recruitment needs, reduce attrition from the delayed entry group, and spread the training schedule more equally across the three years. In order to have a better understanding of general function in the chronic stage of recovery for this moderately to severely impaired cohort we will conduct weekly phone calls to the delayed entry group during the 6 week control period and record general activity (household or community) and monitor amount and intensity of arm use. After serving as a control, this group will be randomized to one of the two active interventions.

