Participants and caregivers consenting to the option of videoconferencing with the study team via the VA's "VA Video Connect" app, in addition to the VA's MyHealtheVet website described above, will be trained for approximately 5 to 10 minutes on how to use this app when they receive training on how to use the MyHealtheVet website. The "VA Video Connect" app uses encryption to ensure a secure and private session, and it allows quick and easy health care access from any mobile or web-based device; more information on this app is at <https://mobile.va.gov/app/va-video-connect>. Adding the option for videoconferencing communications via the VA's "VA Video Connect" app would allow for an additional means of communication for participants randomized to the home-based telerehabilitation group--besides just phone calls and asynchronous private messages sent back and forth on the MyHealtheVet website. Videoconferencing communications also would allow for these participants and study team members to, in real time, ensure that participants are completing rehabilitation interventions at home properly.

Participants and caregivers consenting to the option of taking part in the VA MyHealtheVet Secure Messaging Pilot study will be seen for baseline Standard Evaluations (eHeals, Web-based Self-Efficacy & MoCA, Post-training Interviews) following randomization and prior to initiation of the study intervention. Those randomized to the Home-based telerehabilitation will receiving training in the appropriate use of MHV secure messaging for research communication and will be interviewed immediately after training to ensure that they feel confident in their ability to use the MHV portal and secure messaging to communicate with the research team via the BAL-RESEARCH-TELEBATRAC STUDY_RES secure messaging mail group link (see uploaded Interview Form in Section 5.0)

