evaluations in the same time intervals as those receiving active interventions and weekly phone calls to record general activity level. During this time frame, this group may participate in the MyHealtheVet Secure Messaging Pilot to receive the pilot pre and post evaluations and interviews. Every effort will be made for MyHealtheVet Secure Messaging Pilot appointments to be coordinated with the Primary Study appointments to avoid undue travel. After serving as a control, this group will be entered into their delayed active intervention group of either lab-based BATRAC + TTT training, or Lab-based Robot+ TTT.

3 * Describe the relevant prior experience and gaps in current knowledge. Describe any relevant preliminary data:

Expanding the continuum of care to home has significant barriers due to limited opportunity for education, and limited access to rehabilitation professionals which may lead to poor adherence to the rehabilitation program. These barriers can potentially be addressed using modern telemedicine technologies already established at the VA for aspects of healthcare management on their MyHealtheVet website. This will act as a resource for support and involvement of the caregiver in the exercise program. The benefit of family involvement in recovery of upper extremity motor function has yet to be fully investigated. A qualitative study by Galvin et al. found that family members of stroke survivors were willing to participate in unsupervised exercises but indicated a lack of confidence in assisting with the exercises as one of the barriers (Galvin 2009). Additionally, a recent study by Harris et al. found caregiver involvement to be a significant determining factor in improved arm function over and above initial severity of motor impairment and exercise intensity (Harris 2010). Although there are a growing number of studies evaluating various telerehabilitation interventions in stroke, reports using this potentially promising technology for comprehensive home-based upper limb rehabilitation are limited.

In this project, we seek to objectively assess the impact of a comprehensive patient-centered, home-based upper limb telerehabilitation program augmented with an VA approved asynchronous on-line communication website. Results of the study will provide information on the use of this modern technology to improve care in Veterans with stroke related upper extremity neuromuscular impairments.

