1. eHealth Literacy Scale (eHeals): This is an 8-item questionnaire that measures your perceived ability and comfort using information technology for health. It will be used to gain an understanding of your electronic health literacy at the beginning and again at the end of the study. It should take approximately 5 minutes to complete.

2. Web-Based Learning Self-Efficacy Scale (WBLSES): This is an 8 to 12 item questionnaire used to rate your confidence using electronic tools for web-based online learning. Questions ask you to rate your opinion the MyHealtheVet instructions used, availability of assistance, amount of time available to complete the items, encouragement, physical conditions and computer navigation methods. It will be given at the outset of the study and again at the end of the study. It should take approximately 5 minutes to complete.

3. Montreal Cognitive Assessment (MoCA): The Montreal Cognitive Assessment is a 30-point screening instrument that has been validated to detect mild cognitive impairments or deficits in attention, memory, learning and visuospatial functions that may be due to neurological deficits consistent with stroke. The MoCA will be used to gain a general baseline of study participant's cognitive functioning and should take no more than 20 minutes to complete.

4. Interview: Post-training interviews will be completed after you receive instruction in using the MHV website for access to the secure messaging portal and mail group. This interview will be completed after your initial instruction and at any follow-up training. Questions will focus on your experience with the training and confidence using the site.

Qualitative Study Additional Procedures

1. Background Questionnaire: There are two versions of the background questionnaire; one designed for a study participant and one for staff and lab personnel employed by the VA Maryland Health Care System or University of Maryland. This is an 8-12 item questionnaire used to gather the study participants', staffs' or lab personnel's prior experience with the My HealtheVet patient portal and its tools prior to using it and or being involved in the design and implementation in the My HealtheVet Secure Messaging Pilot Study. It should take approximately 5 minutes to complete.

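### Pilot Aim 3 and Aim 4 Hypothesis 1 read the home group's rise over its own baseline as efficacy, although randomised delayed-entry participants may complete the same scales

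*Combined protocol and SAP*

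**What the plan says.** All references are to the combined protocol and SAP.

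- **Aim 3** (*Justification, Objective, & Research Design*, item 1, pilot aims and hypotheses) is to "Determine efficacy of the two (2) one-hour structured MHV training on stroke survivors and caregivers Web-Based Learning Self-Efficacy Scores (WBLSES) and eHEALS scales". Hypothesis 1 is that the home "intervention group WBLSES will exceed the baseline scores at the end of the clinical trial". Hypothesis 2 is that the same group's "eHEALS Health Literacy Scale will exceed the baseline scores at the end of the clinical trial".
- **Aim 4** is to "Determine efficacy of stroke survivors and caregivers use of the MHV patient portal and Secure Messaging for communication with research team". Hypothesis 1 is that home-group "WBLSES and eHeals literacy scores will increase from baseline demonstrating improved comfort and skill". Hypothesis 2 is that the home group's message volume rises over the study. None of these four hypotheses names a comparator.
- **Aim 2** compares home with delayed entry on both scales. It asks only that home scores be no lower than control scores.
- **Who is in the pilot** (item 2, research design): participants and caregivers opt in at consent, before allocation. They join the pilot if the participant is randomised to home or delayed entry. The lab arm is left out.
- **Controls** (*Delayed Entry Usual Care*): during the control period "this group may participate in the MyHealtheVet Secure Messaging Pilot to receive the pilot pre and post evaluations and interviews". *Study Procedures* reserves the portal training for the home group.
- **Timing:** pilot baselines are taken "following randomization and prior to initiation of the study intervention" (*Intervention and Training*). Of the WBLSES, *Study Procedures* says: "It will be given at the outset of the study and again at the end of the study".
- **Analysis plan:** *Sample Size and Data Analysis* covers the two WMFT aims and gives no analysis for the pilot scales.

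**The concern.** A conclusion about efficacy needs some account of what would have happened without the training. A home-group rise over its own baseline gives none. Familiarity with the questionnaires, the passage of time and general contact with the trial can all raise self-rated confidence, and each would be counted as an effect of the training or the portal. The delayed-entry opt-ins offer a randomised comparison on the same scales over six weeks, so the weakness is avoidable.

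The stake is limited but real. The pilot is an optional sub-study and the WMFT primary aim is untouched. Its findings are, however, meant to feed later VA policy on secure messaging in research, and a statement that the training works would be an attractive one to carry forward.

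**Working it through.** The plan states no sample size, SD, alpha or power for the pilot scales, so there is no figure to reproduce. The check has two parts: what each contrast estimates, and an illustration under stated assumptions.

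**1. What each contrast estimates.** Let τ be the true effect of the home programme and g the change that would occur in both groups anyway.

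- Home group, post minus baseline: τ + g.
- Home change minus delayed-entry change: (τ + g) − g = τ.

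The pre-post contrast passes g on in full. The between-group contrast removes it.

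**2. Whether Aim 2 catches the error.** Set τ = 0 and g > 0, with both groups starting at μ. Both finish at μ + g. Home is above its own baseline, so Aim 3 and Aim 4 Hypothesis 1 are met. Home equals control, so Aim 2 is met too. All would be reported as supported with no training effect.

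**3. Illustration.** Assumptions:

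- n = 22 home participants. This is the parent trial's planned completers per group, an upper limit because the pilot is optional; caregivers are not counted. n = 11 shows a half-size pilot.
- Paired t test, two-sided 0.05, τ = 0.
- Drift d in SDs of the change score, assumed.

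The test statistic has n − 1 degrees of freedom and noncentrality d√n. For n = 22, √22 = 4.690, so d = 0.3 gives 1.407 and d = 0.5 gives 2.345.

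| Assumed shared drift (SD) | Significant rise, home only, n = 22 | Same, n = 11 | Home vs control change |
|---|---|---|---|
| 0 | 2.5% | 2.5% | 2.5% |
| 0.2 | 14.4% | 8.7% | 2.5% |
| 0.3 | 26.9% | 14.5% | 2.5% |
| 0.5 | 60.9% | 32.3% | 2.5% |
| 0.8 | 94.7% | 66.8% | 2.5% |

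The last column is the chance of a significant result favouring home. It stays at 2.5% because the noncentrality is zero for any shared drift.

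**4. What the between-group contrast costs in precision.** The standard error of a one-group mean change is SD/√n, or 1/√22 = 0.213 SD. For a difference in mean change it is SD√(2/n), or √(2/22) = 0.302 SD, which is √2 = 1.41 times larger. At two-sided 0.05 the between-group test has 80% power for about 0.87 SD with 22 per arm and about 1.26 SD with 11 per arm.

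**The case against.** The strongest reply is that the randomised comparison already exists in Aim 2, and that comparing post scores between randomised groups is valid without using change. That is true of the contrast. It does not rescue Aims 3 and 4, because their efficacy conclusions are not tied to Aim 2 and equal scores satisfy Aim 2.

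A second reply is that the *Research Protocol* page lists a separate pilot protocol, which is not available here and may hold the analysis. This stands as a limit: what can be shown is how the hypotheses are worded, not how the data will be analysed. The hypotheses still need correcting.

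Third, the control comparison does less than one might hope. Home differs from delayed entry by the whole telerehabilitation package, not only the portal training. Delayed-entry participants know they are waiting, so expectation differs between arms and does not cancel. Some WBLSES items ask about the portal instructions and the help available, which untrained controls can hardly rate. All of this stands and limits the wording of any conclusion.

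Three stronger readings are tempting but not supported:

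- **Regression to the mean.** A reader might add it to the list of spurious gains. No eligibility criterion selects on eHEALS or WBLSES, so the documents give no reason to expect it.
- **Post-allocation baselines inflate the gain.** If knowing the allocation raises home participants' baseline confidence, the pre-post gain shrinks. The late baseline is a reason for caution, not evidence of bias towards efficacy.
- **Controls certainly cross over to home training.** The research design text says they are randomised to one of the two active interventions. *Delayed Entry Usual Care* names two lab-based options. These passages conflict and must be reconciled. A comparison made before controls start training does not depend on the answer.

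**Conclusion.** The point holds for Aim 3 (both hypotheses) and Aim 4 Hypothesis 1. As worded, they would count time and retest effects shared by both groups as efficacy while a randomised control on the same scales goes unused, and Aim 2 would not reveal the error. Aim 4 Hypothesis 2 is also uncontrolled, but controls have no counterpart for message volume, so it can only be descriptive.

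The size cannot be fixed from the documents. The 27% to 61% range at 22 participants rests on an assumed drift of 0.3 to 0.5 SD. It shows the consequence of such a drift, not that one is likely. That participants know their allocation is inferred: the trial is single blind with a blinded evaluator, and home training cannot be mistaken for a six-week wait.

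This should be corrected, but it is confined to a sub-study and does not affect the trial's main comparisons.

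**What to change.** **Main change.** For Aim 3 and Aim 4 Hypothesis 1, define the efficacy estimate as the home versus delayed-entry difference in change (or in baseline-adjusted score) on eHEALS and WBLSES. Report it with a confidence interval, at the training-completion or week-6 visit and before any control starts active training. Home training may stretch to nine weeks, so state how the timing of the two arms is aligned. Report the home group's end-of-study rise and its message volume as descriptive only.

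**Wording of conclusions.** State that the contrast reflects the whole home package, that differing expectation is not removed, and that WBLSES items about the portal instructions are hard to interpret in untrained controls.

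**Preferred addition.** Collect both scales at the existing baseline visit, before randomisation, from everyone who opts in.

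**Reconcile** the two descriptions of what controls receive after the delay.

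**Cost.** The main change needs revised wording and one added administration of about 10 minutes (two 5-minute scales) in the home arm at a visit already scheduled. Its statistical price is the lower precision shown above, which argues for an interval rather than a bare test. Earlier baselines add about 10 minutes for each opt-in later allocated to the lab arm: at most 78/3 = 26 participants, plus their opt-in caregivers. They also require changes to the consent form and to the text that keeps the lab arm out of the pilot.

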During the pilot, a designated member of the research team will train, and re-train if necessary, on the importance of directing clinical messages to one of their clinical teams and research messages to the research team at the BAL-RESEARCH-TELEBATRAC STUDY_RES secure messaging mail group. Reinforcement to direct all research communications to the research team (BAL-RESEARCH-TELEBATRAC STUDY_RES) will also be provided. The Veteran study participant's knowledge will be reassessed to ensure understanding of how to submit research related secure messages to the BAL-RESEARCH-TELEBATRAC STUDY_RES secure messaging mail group and non-urgent clinical communications to their health care provider(s) using a questionnaire and misdirected communication will be tracked and re-directed.

The VA MyHealtheVet website will allow for asynchronous communication with the participant and therapist to promote personalized prescription of the BATRAC arm exercise. All telerehab interventions will occur at home with entry into the MyHealtheVet by the participant and/or caregiver on their preferred electronic device or on a VA provided touchscreen tablet. The individualized BATRAC exercise protocol will be the same for both groups, however the Home Telerehabilitation group will use this asynchronous communication to guide their exercise program.

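### Three secure messaging pilot hypotheses read higher eHEALS or WBLSES scores as improved skill, but both scales are self-ratings and cannot show skill

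*Combined protocol and SAP*

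**What the plan says.** The pilot aims are in the Justification, Objective, & Research Design section, item 1. Four hypotheses there speak of comfort and skill:

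- Aim 3 Hypothesis 1, on the portal: "WBLSES will exceed the baseline scores at the end of the clinical trial demonstrating improved comfort and skill in using the MHV patient portal".
- Aim 3 Hypothesis 2, on secure messaging, reads a rise in eHEALS as "demonstrating improved comfort and skill in using secure messaging for health care management".
- Aim 4 Hypothesis 1, on portal and secure messaging: "WBLSES and eHeals literacy scores will increase from baseline demonstrating improved comfort and skill in the use of the MHV patient portal".
- Aim 4 Hypothesis 2, on use over time: "secure messaging volume will increase over the 18 week period of the study demonstrating improved comfort and skill in the use of secure messaging".

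The Study Procedures section, under the additional pilot procedures, describes the instruments. eHEALS "measures your perceived ability and comfort using information technology for health". WBLSES is "used to rate your confidence using electronic tools for web-based online learning", and it also asks for opinions on the MyHealtheVet instructions, help available, time, encouragement, physical conditions and navigation.

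Item 2 of the Justification section, under Intervention and Training, adds that the Veteran participant's knowledge of where to send research and clinical messages is reassessed "using a questionnaire and misdirected communication will be tracked and re-directed".

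**The concern.** A self-rating shows how able or confident someone feels. It does not show whether that person can send a secure message, or send it to the right team. Three hypotheses nevertheless commit the pilot to a skill conclusion if the ratings rise.

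The pilot is intended to inform future VA research policy. Item 1 lists message management, ease of reassignment and unintended consequences among the matters to be assessed, and item 2 makes correct separation of research from clinical messages a training objective. Followed as written, the plan could report improved skill while routing errors continue. It could also report no gain among people who route messages correctly but rate their confidence the same as before. Both arise from the choice of measure, whatever the comparison group or visit timing.

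**Working it through.** No arithmetic underlies the main point. The document gives no sample size, power or analysis for the pilot; the Sample Size and Data Analysis section concerns WMFT only. The check sets each skill claim beside the measure used for it.

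| Hypothesis | Measure | Skill claimed in | Nature of measure |
|---|---|---|---|
| Aim 3 H1 | WBLSES | patient portal | self-rating |
| Aim 3 H2 | eHEALS | secure messaging | self-rating |
| Aim 4 H1 | WBLSES and eHEALS | portal and secure messaging | self-rating |
| Aim 4 H2 | message volume | secure messaging | observed use |

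So 3 of the 4 hypotheses that claim skill rest on self-ratings alone.

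The plan contains three measures that do not depend on self-rating: message volume, the routing-knowledge questionnaire and the tracking of misdirected messages. One is in a hypothesis and two are not. The post-training interview does not fill the gap, because its questions cover experience of the training and confidence with the site.

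**Does volume support the skill claim?** Only weakly.

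1. Item 2 asks for a report form, attached to the secure message, after every exercise session. There are 3 sessions × 6 weeks = 18 sessions, spread over at most 9 weeks.
2. If each form is returned by secure message (an assumption, since the return route is not spelled out), this stream runs at 18/6 = 3 per week, or 18/9 = 2 per week at the slowest schedule.
3. Training then stops for 8 weeks before the retention visit, and the stream falls to 0 per week.

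Volume therefore partly reflects the schedule. A count of messages also does not show whether each went to the right team.

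**Could the two unassigned measures show improved skill?** Not as the plan describes them.

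- No routing score or misdirection count before training is described, so there is no baseline for a change.
- Misdirected messages are tracked, but the document does not say that the study obtains each person's total of messages sent, including those to clinical teams. The VSSC counts under Research Related Risks carry no identifiable information.
- Knowledge reassessment is stated for the Veteran participant only, whereas the hypotheses cover survivors and caregivers.
- Retraining where needed and redirection of misdirected messages take place during follow-up, so they alter what is later observed.

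These measures can describe correct use after training. They cannot show improvement.

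**The case against.** The strongest reply is that, for Aim 3, this is a point of wording. Aim 3 is defined as the effect of training on the two scale scores, so the scales are the stated endpoints and the clause about skill is interpretation. Changing it alters no estimate or test. That is correct, but the clause fixes what the pilot will say it found, and the measures do not support it.

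Further replies stand in part:

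- WBLSES is not purely a measure of general web confidence. Some of its items concern MyHealtheVet instructions and navigation. These are still ratings.
- Misdirected messages would not go unnoticed. They are tracked and redirected, users are retrained where needed, and interviews and an optional focus group gather experience. These routes can inform policy, but they do not turn a self-rating into evidence of skill.
- The Research Protocol page lists a separately uploaded pilot and qualitative study protocol that is not part of the document reviewed. It may name further outcomes, so the statement that no hypothesis uses the two measures is limited to the text available.

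A reader might infer that every direct measure has been left out of the hypotheses. The document does not support this, because Aim 4 Hypothesis 2 uses message volume. Nor do all three scale-based hypotheses concern secure messaging: Aim 3 Hypothesis 1 concerns the portal.

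A reader might also multiply 18 session reports by the number of home participants and treat the product as a sample of routing decisions. The reports are forms attached to the message. If they come back as replies, addressing is not tested, and nothing shows them to be independent decisions about where to send a message.

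**Conclusion.** The point holds, within limits. Aim 3 Hypotheses 1 and 2 and Aim 4 Hypothesis 1 draw a conclusion about skill that eHEALS and WBLSES, as the protocol describes them, cannot support. Comfort and confidence are supportable. The one observed measure in a hypothesis, message volume, measures use and partly follows the session schedule. Two measures closer to skill have no assigned role in the document reviewed.

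The effect is on what an optional sub-study can conclude. The WMFT aims, their sample size and their analyses are untouched. The conclusion rests on the protocol's own descriptions of the two scales and on the pilot hypotheses as they appear in this document.

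**What to change.** 1. Reword Aim 3 Hypotheses 1 and 2 and Aim 4 Hypothesis 1 so that a rise in WBLSES or eHEALS supports a conclusion about self-perceived ability, comfort and confidence only.
2. Under Aim 4, report descriptively, as evidence of correct use after training and not of improvement:
   - the count of misdirected messages per participant, given as a proportion of messages sent only if the study can obtain that denominator;
   - the routing-knowledge result, for the participants who are reassessed, stating who they are and whether caregivers are included.
3. State beside these results that retraining and redirection occur during follow-up.
4. Check the separately uploaded pilot protocol and bring its wording into line.

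The cost is a change to three hypotheses and a short descriptive summary of data already planned. The count needs no new procedure; a proportion would need the message total. The downside is that the pilot's claim about skill becomes narrower.
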